15.1. General Considerations

Descriptive summaries of variables will be provided where appropriate. For continuous variables, the number of non-missing values (n) and the median, mean, standard deviation, minimum, and maximum will be tabulated. For categorical variables, the counts and proportions of each value will be tabulated. Confidence intervals will also be provided as appropriate. All statistical tests will be performed at the 0.05 level.

Further details on all analyses will be provided in the statistical analysis plan (SAP).

15.2. Sample Size Estimation

The sample size of Part A has been chosen on pragmatic grounds to be approximately 75 study patients. The number of patients ultimately included in Part A will be decided by the Steering Committee and the Sponsor based on the perceived understanding of the protocol by clinical sites and the feedback obtained during the Part A training phase. Part A will not be randomized; all study patients in Part A will receive PD G 506 A. Data acquired from Part A will be used to confirm the Investigators' understanding of fluorescence guided resection (FGR) procedures in the protocol and to confirm the sample size for Part B. Only data from participants in Part B will be used for the analyses of primary and secondary efficacy. Data from all patients in both Part A and Part B will be used for the evaluation of safety and analyses will include assessments of data from Part A and Part B separately, as well as all study patients (Part A and Part B together).

P(1.1) Conversion Rate among all patients =

patients with at least one histopathology-positive margin following SoC and histopathology negative final margins after FGR

All patients imaged (Arm 2)

SBI-CIP 20-002 Rev: v1.8 A prospective multi-center clinical study evaluating the use of PD G 506 A and the Eagle V1.2 Imaging System for the visualization of carcinoma during breast conserving surgery	Page: 96 of 157
---	-----------------

The sample size in Part B of the study is only driven by the primary endpoint P(1.1). The primary endpoint is intended to determine the percentage of patients with at least one histopathology-positive margin after SoC who then have all histopathology-negative margins after FGR (conversion rate among all patients in Arm 2). To demonstrate benefit, the point estimate P(1.1) must be statistically significantly greater than 1%. By meeting this primary endpoint, we will demonstrate that FGR adds clinical benefit above and beyond what is achieved with SoC.

Based on the expected 3% conversion rate estimate for P(1.1), a total of 500 patients will be required in Part B of the study to demonstrate statistical significance at a Type 1 error level of 0.05 with 90% power using a 2-sided Z test for a binomial proportion assuming a null hypothesis proportion of 1%.

Using a randomization ratio of 1:6 (Arm 1-SoC; Arm 2: PD G 506 A), a total sample size of 525 patients (Arm 1: N=72; Arm 2: N=428) would be required, accounting for a 5% loss to follow-up. The primary efficacy analysis will be based on the mITT (modified intention-to-treat population), which includes all Part B patients randomized to Arm 2 who undergo surgery and have recorded surgical histopathology data.

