Final Margin(s)	Final margin is comprised of the outside surface of the last resected tissue(s) for each anatomical surface and the final cavity at that margin. Final margins are evaluated to determine whether the patient has positive or negative margins based on postoperative clinical pathology assessment. For each patient, final margins after SoC and final margins after FGR will be evaluated histopathologically. If there are no FL-driven cavity shave specimens collected in a patient randomized to receive FGR , then the final margins after FGR are equivalent to the final margins after SoC .			
Positive Margins	Surgical Oncology as follows:			
		Surface histo	pathology status Positive	Negative
True Positive Orientation	Surface fluorescence	Positive	True positive (TP)	False positive (FP)
	status	Negative	False Negative (FN)	True Negative (TN)
and True Negative Orientation	a. A TP orientation contains at least 1 True Positive surface. b. A FN orientation contains at least 1 False Negative surface and no True Positive surface. c. A FP orientation contains at least 1 False Positive surface and no True Positive or False Negative surfaces. d. A TN orientation contains only True Negative surfaces.			

SBI-CIP	Rev: v1.8	A prospective multi-center clinical study evaluating the use of PD G 506 A and the Eagle V1.2 Imaging System for the visualization of	Page: 18 of 157
20-002	V1.0	carcinoma during breast conserving surgery	

Re-excisions

A re-excision is defined as a surgical procedure performed in the ipsilateral breast following the primary lumpectomy because of positive margins found from the initial lumpectomy procedure. The re-excision procedure can be a separate surgical procedure to excise further breast tissue or a mastectomy.

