6.2.5. Anticipated clinical benefit

Study patients who receive PD G 506 A (i.e., all participants in Part A and Part B patients randomized to Arm 2) may experience a clinical benefit as a result of their participation in the study. Arm 2 patients with residual carcinoma in the cavity or on the *final margins after SoC* may have the residual carcinoma in the cavity resected and/or the final margins converted from carcinoma-positive after SoC to carcinoma-negative as a result of *FGR*. If *FGR* improves (decreases) the positive margin rate after surgery, Arm 2 patients may also benefit from not having to undergo a second surgery to achieve negative margins.

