7.1. Primary Objective and Endpoint

Primary	Primary Endpoint					
Objective	Parameter Description	Parameter Formula		Abbreviated Description		
1.To evaluate the efficacy of PD G 506 A by demonstrating the clinical usefulness of PDG 506A to identify additional malignant breast tissue during BCS after SoC	Percentage of patients with at least one histopathology-positive margin following SoC who then have ALL histopathologynegative margins following FGR, among all patients imaged.	P(1.1) Conversion Rate = # patients with at least one histopathology-positive margin following SoC and histopathology negative final margins after FGR All patients imaged (Arm 2)	x 100%	Conversion rate among all patients		

	SBI-CIP 20-002	Rev: v1.8	A prospective multi-center clinical study evaluating the use of PD G 506 A and the Eagle V1.2 Imaging System for the visualization of carcinoma during breast conserving surgery	Page: 28 of 157
--	-----------------------	--------------	--	-----------------

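### P(1.1) counts only positive-to-negative margin conversions and no endpoint isolates or nets the reverse change, so meeting P(1.1) does not by itself show benefit beyond SoC

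*Combined protocol and SAP*

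**What the plan says.** Section 7.1 defines the P(1.1) numerator as patients with at least one "histopathology-positive margin following SoC and histopathology negative final margins after FGR", over all imaged Arm 2 patients. Section 15.6.1 labels these patients a clinical success. It labels as clinical failure only those who are positive after SoC and still positive after FGR. A patient who is negative after SoC and positive after FGR has no label and sits in the denominator as a non-event.

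Section 5.1 (Final Margin(s)) defines the final margin through the outside surface of the last tissue resected at each anatomical location, and adds: "Final margins are evaluated to determine whether the patient has positive or negative margins based on postoperative clinical pathology assessment". Both the margins after SoC and the margins after FGR are read for each patient.

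Section 15.2 sizes Part B on P(1.1) alone: "Based on the expected 3% conversion rate estimate for P(1.1), a total of 500 patients will be required in Part B". It then draws the inference "By meeting this primary endpoint, we will demonstrate that FGR adds clinical benefit above and beyond what is achieved with SoC". Section 6.2.5 describes the possible benefit to patients in different terms, conditional on FGR being something that "improves (decreases) the positive margin rate after surgery".

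**The concern.** An FL-driven shave replaces the SoC margin at that location. It is taken because of fluorescence, when the SoC histology is not yet known. If its outer surface carries carcinoma, a patient who would have left surgery with negative margins leaves with a positive one. The positive-margin rate after FGR therefore depends on two flows, conversions and reversals, and P(1.1) sees only the first.

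The key secondary endpoints do not close the gap. P(2.1) is restricted to SoC-positive patients, and P(2.2) and P(2.3) are assessed at the end of SoC. At stake is the conclusion drawn from a positive trial: the 15.2 sentence goes from a conversion rate above 1% to a benefit over SoC, with no reported figure showing whether reversals offset the conversions.

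**Working it through.** **Inputs.** Null 1%, expected 3%, tested "at a Type 1 error level of 0.05 with 90% power using a 2-sided Z test for a binomial proportion" (15.2). Arm 2 N = 428, Arm 1 N = 72 (15.2). Success if the Wilson 95% lower bound exceeds 1% (15.6.1). Expected P(2.1) above 15% (15.6.2). No document gives a reversal rate, so reversals are an assumption, varied below.

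**The plan's own figure.** n = [(1.960 x sqrt(0.01 x 0.99) + 1.282 x sqrt(0.03 x 0.97)) / 0.02]^2 = 427.7, so 428 in Arm 2. 428 x 7/6 = 499.3, so 500 in total, and 500 x 1.05 = 525. The sample size reproduces.

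**What P(1.1) needs.** At n = 428 the Wilson lower bound is 0.95% for 8 conversions and 1.11% for 9, so success starts at 9 (2.10%). Exact power at 3% is 89.6%. The planned 3% is 428 x 0.03 = 12.8, or 13 conversions (Wilson 1.78% to 5.13%).

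**Net change.** Let b be conversions and c reversals. Net fall = (b - c)/428, with Wald SE = sqrt(b + c - (b - c)^2/428)/428. The p-value is exact McNemar, a binomial test of b out of b + c against 1/2. For b = 13, c = 7: 6/428 = 1.40%, SE = sqrt(20 - 36/428)/428 = 1.043%, interval -0.64% to 3.45%.

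| b | c (assumed) | P(1.1) succeeds | Net fall, points | McNemar p |
|---|---|---|---|---|
| 9 | 0 | yes | 2.10 | 0.004 |
| 9 | 4 | yes | 1.17 | 0.27 |
| 9 | 9 | yes | 0 | 1.00 |
| 13 | 4 | yes | 2.10 (0.23 to 3.98) | 0.049 |
| 13 | 7 | yes | 1.40 (-0.64 to 3.45) | 0.26 |
| 13 | 13 | yes | 0 | 1.00 |
| 13 | 15 | yes | -0.47 (a rise) | 0.85 |

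**Scale.** If P(1.1) = 3% and P(2.1) = 15%, about 3/15 = 20% of patients are SoC-positive: roughly 86 positive and 342 negative. Nine reversals are then 9/342 = 2.6% of SoC-negative patients, and thirteen are 13/342 = 3.8%. The 20% is inferred from two expected values, not stated.

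**Power for the net change.** With a 3% conversion rate, exact McNemar power is 99% if no patients reverse, 90% at a reversal rate of 0.25% of all patients, 77% at 0.5%, 47% at 1% and 10% at 2%. Power for P(1.1) is 89.6% throughout. The net change can therefore be supportive only, not a second gate.

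**Endpoints that include these patients.**
- P(2.6): at the end of FGR, histology is the outside surface of the last specimen (15.4.4). TP plus FN patients are then all patients with a positive final margin, old and new together.
- P(2.9): only those who are also fluorescence-negative at the end of FGR.
- P(2.11): SoC-negative patients in whom FGR found carcinoma, counted as detections whatever the final margin.
- P(2.15), P(2.16): re-operation by arm, compared by Fisher's exact test (15.7). This is an indirect net comparison, but it depends on a decision to re-operate after the surgeon is unblinded (10.3) and has 72 controls. If every positive margin led to re-operation, 20% against 17% gives pooled p = 0.174, null SE 0.0483 and alternative SE 0.0505. Power is Phi((0.03 - 1.96 x 0.0483)/0.0505) = Phi(-1.28), about 10%.

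**The case against.** The strongest reply is that the information is already there. SoC-positive patients (the P(2.1) denominator) minus TP plus FN patients in P(2.6) equals b - c. So a reader who infers that nothing in the plan counts newly positive patients goes too far. What stands is narrower: no listed endpoint forms that difference, shows c, or gives an interval for it.

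Second, the protocol limits reversals. Shaving repeats while the outer surface of the shave or the cavity fluoresces (12.4.3; Appendix 2, steps 25-27). A reversal needs carcinoma at an outer surface where neither fluoresces, or tissue that cannot be taken further. This stands: reversals may be rare. A reader might try to size them by taking 342 x 20% = 68 SoC-negative patients expected to have a shave at 80% specificity, and applying a reversal rate to them. The documents do not support that. Those 68 are false-positive patients, who at the end of SoC have no positive histology on either facing surface (5.2, 15.4.4.1). Patients with carcinoma on the inner face of the shave are classed as true positives and fall outside the 68.

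Third, the primary objective is to identify additional malignant tissue, and a newly positive margin may be residual disease that SoC missed. Netting it against a conversion scores a true detection as a loss. This also stands, and it argues against making net change the sole basis for a benefit claim. It does not argue against showing it.

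Fourth, section 2 records that the endpoint and the 1% null follow regulatory advice, and 6.2.5 is conditional risk-benefit text rather than an efficacy claim. Both are correct, and neither supports the inference in 15.2. Section 15.1 also defers detail to a separate SAP, which may add a table; the text available here specifies none.

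**Conclusion.** The point holds as a limit on interpretation. P(1.1) is one-directional, the margin definition allows the reverse change, and the success rule can be met with a net change of zero (9 and 9, or 13 and 13) or slightly worse (13 and 15). The 15.2 statement therefore does not follow from P(1.1) alone. No primary or key secondary endpoint counts reversals, and no endpoint isolates them or reports the net change in the positive-margin rate.

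The actual size is unknown. Every value of c above is assumed, and the table shows what the rule permits, not what is expected. The documents do not support reading this as evidence that FGR fails to lower the positive-margin rate, or that P(1.1), its threshold or its sample size is wrong.

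**What to change.** Keep P(1.1), the 1% threshold and the sample size. Then:

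- In 7.2 and 15.7, pre-specify a supportive paired 2x2 table of patient margin status after SoC by status after FGR (Arm 2, mITT). Give both off-diagonal counts and the net change with a paired 95% score interval, with exact McNemar as supportive. State whether the residual-fluorescence rule of 15.6.1 applies to the table, so that its conversions match the P(1.1) numerator.
- For newly positive patients, show how many had carcinoma found in an FL-driven shave and so also count as detections in P(2.11).
- Reword the 15.2 sentence: meeting P(1.1) shows that the rate of favourable conversions exceeds 1%, and any statement about the positive-margin rate is to be read together with the net change.

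The cost is one table and some wording. No new data are needed, because both margin statuses are already read for each patient (5.1) by pathologists blinded to how the samples were obtained (8.3). The downside for the sponsor is that, under the same margin rule, the net figure can be no larger than P(1.1), and the mixed clinical meaning of a newly positive margin will have to be explained.

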11.1. Handling of Participant Withdrawals or Termination

All data collection relating to a withdrawn or terminated participant, excluding safety data for participants that have received PD G 506 A, will cease at the time of withdrawal/termination. Clinical care in all withdrawn or terminated participants will continue as per standard of care.

In order to maintain the required number of study subjects, any participant that withdraws or is terminated prior to completion of the Week 2 visit will be replaced. Participants that withdraw or are terminated after the Week 2 visit but prior to the 1 year follow-up will not be replaced.

SBI-CIP 20-002 Rev: v1.8 A prospective multi-center clinical study evaluating the use of PD G 506 A and the Eagle V1.2 Imaging System for the visualization of carcinoma during breast conserving surgery	Page: 61 of 157
---	-----------------

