In Part B of the study, patients will be randomized in a ratio of 1:6 (Arm 1: N=72; Arm 2: N=428) in up to 20 sites in Canada and the United States. A total of 525 patients would be required, accounting for a 5% loss to follow-up. The primary efficacy analysis will be based on the mITT population, which includes all Part B patients randomized to Arm 2 who undergo surgery and have recorded surgical histopathology data.

Treatment Groups and Duration:

Part A will include up to 75 subjects and will not be randomized; all patients in Part A will receive PD G 506 A.

In Part B, study patients will be randomized 1:6 to:

- Arm 1 (SoC): placebo + conventional BCS (data from this arm will not be analyzed for the primary or secondary efficacy endpoints)
- Arm 2 (experimental): PD G 506 A (20 mg/kg) + conventional BCS + Eagle V1.2
 Imaging System intraoperative assessment

Patients in both arms will be enrolled at the time their index BCS procedure is scheduled and followed until the first post-operative follow-up, approximately 2 weeks (10 - 14 days) after their surgical procedure. A 3-month, 6-month and 1-year follow-up will also be performed.

Investigational Drug: PD G 506 A for oral solution (aminolevulinic acid [ALA] hydrochloride [HCl] granules for oral solution) will be administered as a single dose (20 mg/kg body weight)

SBI-CIP 20-002	Rev: v1.8	A prospective multi-center clinical study evaluating the use of PD G 506 A and the Eagle V1.2 Imaging System for the visualization of carcinoma during breast conserving surgery	Page: 117 of 157

approximately 3 hours (min 2 hours, max 4 hours) prior to anesthesia. PD G 506 A is an optical imaging agent for real-time visualization of carcinoma.

Investigational Device: The Eagle V1.2 Imaging System consists of a handheld, wireless, battery-powered, imaging camera (Handheld Fluorescence Camera) and related accessories. The Handheld Fluorescence Camera has 405 nm and white light illumination light sources and dual imaging sensors with optical filters for imaging of PD G 506 A-induced red PpIX fluorescence and standard full spectrum visible light, respectively.

Study Population: Study patients will be adult female surgical patients with breast cancer undergoing breast conserving surgery.

Inclusion criteria

- 1. Female, 18 years or older

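### The arm sizes printed with the 525 total (72 and 428) add up to 500: they are the numbers before the loss allowance, and 525 at 1:6 is 75 and 450

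*Combined protocol and SAP*

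**What the plan says.** Section 15.2 gives the Part B calculation in two steps.

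- Before loss: "a total of 500 patients will be required in Part B of the study to demonstrate statistical significance", with an expected conversion rate of 3%, a Type 1 error of 0.05, and "with 90% power using a 2-sided Z test for a binomial proportion assuming a null hypothesis proportion of 1" per cent.
- After loss, at 1:6: "a total sample size of 525 patients (Arm 1: N=72; Arm 2: N=428) would be required, accounting for a 5% loss to follow-up".

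The Number of Patients paragraph of the synopsis (Appendix 1) carries both figures. It says that "patients will be randomized in a ratio of 1:6 (Arm 1: N=72; Arm 2: N=428"), and its next sentence but one line on reads "A total of 525 patients would be required, accounting for a 5% loss to follow-up".

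The denominator of the primary endpoint P(1.1) is the imaged patients of Arm 2 only. Section 11.1 adds that "any participant that withdraws or is terminated prior to completion of the Week 2 visit will be replaced".

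**The concern.** The bracket after 525 reads as the breakdown of 525, yet its two entries add to 500. The synopsis goes further: it presents 72 and 428 as the numbers to be randomised and then asks for 525. No section gives arm sizes that add to 525.

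Someone setting up randomisation or tracking accrual therefore meets two Arm 2 targets, 428 and 450, with nothing in the text to say which is the evaluable number and which is the randomised one. If 428 were taken as the randomisation target, the 5% allowance would disappear from the one arm that enters the primary analysis.

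**Working it through.** **Inputs (all Section 15.2).** Null proportion p0 = 0.01; expected proportion p1 = 0.03; two-sided Type 1 error 0.05 (z = 1.96); power 90% (z = 1.2816); one-sample Z test for a proportion; allocation 1:6; loss 5%.

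**1. Reproduce the plan's figure.** With the null variance for the error term and the alternative variance for the power term:

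n = [(1.96·√(p0(1−p0)) + 1.2816·√(p1(1−p1))) / (p1−p0)]²
= [(1.96·√0.0099 + 1.2816·√0.0291) / 0.02]²
= 427.7, rounded up to **428** in Arm 2.

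Arm 1 at 1:6: 428/6 = 71.3, rounded up to **72**. Total: 72 + 428 = **500**.

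This is the pre-loss total in Section 15.2, so 72 and 428 contain no allowance for loss. Other forms were tried: one-sided, 80% power, a single variance in both terms, and a continuity correction. None of them gives 428.

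**2. Reproduce the total after loss.** 500 × 1.05 = **525**. Dividing by the retained fraction instead gives 500/0.95 = 526.3, so 527. The printed 525 therefore comes from multiplying by 1.05.

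**3. Split 525 at 1:6.** 525/7 = **75** and 525 × 6/7 = **450**, both exact.

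| | Arm 1 | Arm 2 | Total |
|---|---|---|---|
| Printed beside 525 | 72 | 428 | 500 |
| 525 at 1:6 | 75 | 450 | 525 |
| Shortfall | 3 | 22 | 25 |

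**4. Power by the plan's Z test.** Power = Φ[(0.02·√n − 1.96·√0.0099) / √0.0291]

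| Arm 2 scenario | Evaluable n | Power |
|---|---|---|
| 428 evaluable, as planned | 428 | 90.0% |
| 450 randomised, 5% lost | 427.5 | 90.0% |
| 428 randomised, 5% lost, none replaced | 406.6 | 88.9% |

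**5. Power under the actual decision rule.** Section 15.6.1 declares success when the lower Wilson bound exceeds 1%. Exact binomial power at a true rate of 3% is:

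| n | Conversions needed | Power |
|---|---|---|
| 406 | 8 | 92.1% |
| 407 | 9 | 86.2% |
| 428 | 9 | 89.6% |
| 450 | 9 | 92.4% |

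Exact power moves in steps, and 406.6 lies on a step. The one-point loss in item 4 is a smooth approximation.

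**The case against.** The case for treating this as trivial has four parts.

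- **The right numbers can be recovered.** The 500, the 525 and the 1:6 ratio are all stated and agree with each other. This is true, but the reader must first work out that the printed arms belong to the other total, and the synopsis wording points the wrong way.
- **Allocation limits the harm.** Randomisation is central, in permuted blocks at 1:6 (Sections 8.1 and 10.2), so enrolling 525 would give about 75 and 450 whatever the bracket says. No section closes an arm at 428. This stands, and the harm depends on someone using 428 as a target.
- **Losses are mostly replaced.** Section 11.1 replaces withdrawals before Week 2 is completed, and Section 12.7 places collection of the efficacy data at that visit. Later loss to follow-up does not touch P(1.1). This also stands in large part. Replacement does not clearly cover a patient who stays in the study but lacks the dosing, imaging or pathology data that Section 15.4.1 requires. If replacement covered every loss, the 525 would lose its stated reason.
- **The size is provisional.** Sections 8.1 and 15.2 and the synopsis let Part A data confirm or determine the Part B size. That limits the practical effect but does not excuse figures that disagree.

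The step pattern in exact power is a fair caution as well: 88.9% should be read as the order of magnitude of the effect. None of these points supplies arm sizes that add to 525.

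**Conclusion.** The inconsistency is real and certain: it rests on addition. The calculation itself is sound, since 428, 500 and 525 each follow from the plan's inputs. The error is that the arm sizes before loss are attached to the total after loss, in Section 15.2 and again in the synopsis. The shortfall is 25 of 525 patients, 22 of them in Arm 2.

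The consequence is small: about one percentage point of Z-test power, and only if 428 became the Arm 2 randomisation target, 5% were lost and none were replaced. It should still be corrected, because these are the planned arm sizes of a pivotal trial and the primary test uses Arm 2 alone.

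**What to change.** In Section 15.2 and in the synopsis, give the evaluable and randomised numbers separately: about 500 evaluable patients (Arm 1 = 72, Arm 2 = 428), and 525 randomised (Arm 1 = 75, Arm 2 = 450), obtained as 500 × 1.05.

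The word *about* is needed because a 5% loss leaves 525 × 0.95 = 498.75 in total and 450 × 0.95 = 427.5 in Arm 2. If the sponsor prefers to keep the full 428 after loss, dividing by 0.95 gives 428/0.95 = 450.5, so 451, and 72/0.95 = 75.8, so 76: a total of 527, two more than now stated.

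The first option costs one sentence in each of two sections. It needs no patients beyond 525 and no change to the test.
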